10 STUDY INTERVENTIONS

Table 3: Study procedure schedule of evaluations

	Visit 1- early hospitalization	Visit 2 – late hospitalization	Visit 3 – after 2 weeks of thiamine repletion
Chart review for social and medical histories	X		
Symptom and function survey		X	X
Targeted physical exam		X	X
Nutritional history		X	
Lab draw for thiamine biomarkers	X		X
Blood draw for prealbumin , others as needed	X		
Thiamine repletion	X ¹	X ²	

1. For select patients with WE or severe symptoms of thiamine deficiency 2. all others

10.1 Visit 1 – initial hospital encounter: The Veteran's chart will be reviewed for acute and chronic medical problems, habits, and social history. We will schedule lab testing (as described below) to coincide with routine morning blood draw to avoid additional phlebotomy. For those who present with symptoms of Wernicke's encephalopathy (WE) which requires urgent parenteral thiamine replacement, we will perform our history and exam promptly and advise the primary inpatient treatment team to initiate therapy if they meet the Caine criteria⁴⁶ for WE. For all others who do not have evidence of WE, we will proceed to visit 2.

Thiamine biomarker and other micronutrient assessment: Fasting plasma thiamine levels and whole blood ThDP will be ordered for collection by lab personnel as soon as feasible after consent is obtained from the Veteran. We will also order blood levels of vitamins B12, D, and folic acid as well as prealbumin if not done via routine care within the preceding four weeks. In addition, we will extract albumin, complete blood count, and magnesium as ordered by the primary team as part of routine care. There will be no genomic sequencing, in whole or in part, as part of this analysis. Blood specimen will be collected as part of routine medical care by laboratory personnel. Lab tests not routinely run in our local laboratory will be sent out to reference labs per the usual practice of the Department of Pathology. There will be no direct handling of blood specimen by the research team. Results of the lab tests will be available in a participant's electronic medical record and will be extracted by the study coordinator and stored in a de-identified database. If they have been prescribed thiamine replenishment and the thiamine lab values are lost, we will include the remaining data gathered in the study.

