10.2 Visit 2 – second hospital encounter: Following stabilization of the acute medical condition(s) for which they presented, the Veteran (and caregiver if the Veteran agrees) will be interviewed and examined by the study's PI or trained advance care practitioner using a standardized checklist of signs and symptoms of TD. We will delay this portion of the assessment until the primary treating team affirms their acute condition has stabilized to avoid misclassification of symptoms from the acute illness with those of TDD. In most cases we anticipate this will occur just prior to hospital discharge. For Veterans with symptoms suggestive of TD, we will provide a prescription for thiamine replacement 100 mg orally daily for two weeks (see **Standardized physical examination and related data**).

Nutritional history: Study personnel will perform a dietary history to adequacy of thiamine intake, recent changes in appetite, food intake or any social or medical risk factors for malnutrition. We will review medical records for acute and chronic medical illnesses that may predispose to malnutrition.

Symptom and function survey: The patient interviews will include questions about the following: acute or worsening symptoms in the following categories: neuropsychiatric (including memory loss, personality or behavior change, psychosis, mood changes, seizures), polyneuropathy (to include muscle weakness, loss of deep tendon reflexes, neuropathic pain, or sensory loss), GI dysfunction (including dysphagia, anorexia, nausea, vomiting, gastroparesis, or constipation), and cardiovascular manifestations (such as palpitations, tachycardia, dyspnea, pulmonary or peripheral edema). We will review recent trends in ability to carry out Basic Activities of Daily Living (ADLs) and Instrumental Activities of Daily Living (IADLs). We will determine if there are symptoms of adult failure to thrive such as weight loss, decreased appetite, inactivity, poor nutrition, depression, loss of functional status as defined by loss of ability to do ADLs or IADLs. We will also ask about medication compliance with both prescribed and over the counter medications and supplements.

Standardized physical examination and related data: We will perform targeted exams for signs of TDDs including mental status exam using the Montreal Cognitive Assessment (MoCA); delirium screen using the 4AT

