clinical test; ophthalmoplegia and nystagmus using the “H” test; evaluations of ataxia, peripheral neuropathy, deep tendon reflexes, and muscle strength using the Medical Research Counsel Adaptation B scale. We will assess for signs of cardiovascular dysfunction such as pulmonary or peripheral edema and tachycardia, and GI signs such as decreased bowel tones. We will assess physical signs of malnutrition including muscle and fat loss and trends in body weight. We will review any existing radiologic studies for evidence of abnormal brain imaging, echocardiogram results, pulmonary edema, or ileus for example.

For patients with severe symptoms such as inability to ambulate, or WE, we will advise the primary treatment team to begin high dose intravenous (IV) thiamine replenishment at 400 mg every eight hours for nine doses while inpatient. In this group we will then prescribe oral thiamine 100 mg once a day after IV therapy is complete until visit 3. For patients with mild-moderate symptoms that could be due to TD, the research pharmacist will process and dispense oral thiamine 100 mg once daily at hospital discharge. If the patient is discharged when the research pharmacist is not at the hospital, the research pharmacist will mail it to the patient on the next business day. Patients who are discharged to skilled nursing facilities, or any other rehabilitation facility, will be contacted by the research team and be medically advised to supplement the patient with oral thiamine 100 mg. We anticipate return of lab biomarker results 7-10 days after they are drawn at which point any individual not identified by clinical screening to have TD will be contacted and oral replenishment initiated. As with the symptom and function survey we will record these findings on a government furnished computer with a paper record as backup.

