10.3 Visit 3 – follow-up of symptomatic Veterans after empiric thiamine treatment. All Veterans with low biomarkers OR low normal biomarkers and clinical symptoms of TDDs that were initiated on replacement will be seen at a follow-up visit 3 after two weeks of thiamine replacement. We will repeat the symptom and function survey and repeat the standardized physical assessment. We will categorize changes in symptoms and signs as *no or minimal improvement, or noticeable improvement*. We will re-order thiamine biomarkers to assess for increases in levels. We will recommend continued dosing with thiamine 100 mg daily thereafter for any Veteran with improvement in their symptoms and update their medical record to include thiamine deficiency in their problem list. If a participant failed to complete the 2 weeks of replenishment, we will provide another 2-week course of replenishment and reschedule this visit.

Study Duration/ Study Timeline:

See Table 3. We expect visit 1 will not take substantial time for the Veteran. Visits 2 and 3 will take between 60 and 90 minutes each. For Veterans without symptoms of TD, their participation will be complete after visit 2, before discharge from the hospital. For Veterans with symptoms of TD their participation will be complete after taking thiamine for 2 weeks and attending visit 3. We anticipate the study will end 24 months.

Study Endpoints:

Our primary endpoint will be determining prevalence of TD in our Veteran population. We do not anticipate stopping the study before 300 Veterans are recruited. Thiamine supplements are very safe with few side effects, so we do not anticipate stopping early for safety concerns.

Study Locations:

The study will be conducted at the VA Sierra Nevada Healthcare System Hospital inpatient units at [name]. Follow up visits will occur on the ground floor of the hospital in the research department exam rooms.

International Research:

We will not be conducting this research in international locations.

Participant Compensation:

Those that agree to participate will be compensated \$30 for visits 1 and 2 and \$200 if they attend visit 3 after discharge.

Economic Burden to Participants:

Veterans will not incur any costs because of participating in this study. Those that attend the follow up visit will incur the cost of transportation, but this will be mitigated by the \$200 compensation.

Risk to Participants:

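### Section 10.3 adds a biomarker condition to Visit 3 that other sections lack; used as a filter, it would select the exploratory Aim 2 cut-point sample on the marker under study

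*Combined protocol and SAP*

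**What the plan says.** All references are to the combined protocol and SAP.

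- **Section 10.3, sentence on attendance:** "All Veterans with low biomarkers OR low normal biomarkers and clinical symptoms of TDDs that were initiated on replacement will be seen" at Visit 3. Change in symptoms and signs is graded there.
- **Section 10.3, heading:** "follow-up of symptomatic Veterans after empiric thiamine treatment".
- **Study Duration/Study Timeline:** "For Veterans with symptoms of TD their participation will be complete after taking thiamine for 2 weeks and attending visit 3", and "For Veterans without symptoms of TD, their participation will be complete after visit 2, before discharge from the hospital".
- **Data and Specimen Banking:** the survey and examination are repeated at Visit 3 for symptomatic Veterans started on repletion. No biomarker is mentioned.
- **Informed Consent Process:** Veterans suspected of deficiency on symptoms or examination are prescribed thiamine and followed for improvement. Again no biomarker is mentioned.
- **Table 3:** Visit 3 is timed "after 2 weeks of thiamine repletion".
- **Section 10.2:** treatment starts on symptoms ("For Veterans with symptoms suggestive of TD, we will provide a prescription for thiamine replacement"). The severe group continues oral thiamine "after IV therapy is complete until visit 3". On the laboratory: "We anticipate return of lab biomarker results 7-10 days after they are drawn".
- **Section 15.2:** for each of the two thiamine markers, the Liu method finds the cut-point separating responsive from non-responsive symptoms. AUC, sensitivity, specificity, predictive values and likelihood ratio follow. The aim is called exploratory, and no analysis set is named.

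**The concern.** The 10.3 sentence asks for symptoms and started replacement, as the other sections do, but adds a low or low-normal biomarker. A symptomatic, treated Veteran with normal levels is due at Visit 3 under Study Duration and is not on the 10.3 list.

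Such Veterans will exist, because thiamine is prescribed on symptoms before results are back. Results can arrive before a visit held after two weeks of treatment, so staff could apply the sentence as a filter.

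The response grade given at Visit 3 is the reference standard for the Aim 2 cut-points. If receiving that grade depends on the marker being evaluated, the result is partial verification. The comparison group is thinned at its upper end, and the reported accuracy describes only those seen.

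**Working it through.** **1. The rules side by side**

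| Place | Symptoms | Treatment | Biomarker |
|---|---|---|---|
| 10.3 sentence | named | started | low or low-normal |
| 10.3 heading | named | empiric | none |
| Study Duration | named | two weeks taken | none |
| Data and Specimen Banking | named | started | none |
| Informed Consent Process | symptoms and/or examination | prescribed | none |
| Table 3 | not stated | timing only | none |
| 10.2, severe group | severe | duration to Visit 3 | none |

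The 10.3 sentence has two parses: (low) or (low-normal with symptoms), and (low or low-normal) with symptoms. Neither lists a symptomatic treated Veteran who is normal on both markers. The first parse also brings back Veterans with low results and no symptoms, whose participation Study Duration ends at Visit 2.

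**2. The plan's own figure**

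Section 15.2 gives 19 responders and 38 non-responders for AUC 0.725 against 0.50, at alpha 0.05 and 80% power (printed as beta 0.80). The Hanley-McNeil variance is [A(1−A) + (n₁−1)(Q₁−A²) + (n₂−1)(Q₂−A²)]/(n₁n₂), with Q₁ = A/(2−A) and Q₂ = 2A²/(1+A).

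- Null: (0.25 + 18×0.0833 + 37×0.0833)/722 = 0.00669, SE 0.0818.
- Alternative: Q₁ = 0.5686, Q₂ = 0.6094, A² = 0.5256. Variance (0.1994 + 18×0.0430 + 37×0.0838)/722 = 0.00564, SE 0.0751.
- Power, two-sided: Φ[(0.225 − 1.96×0.0818)/0.0751] = Φ(0.86) = 80.5%.

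The figure is reproduced. It allows for no selection on the marker.

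**3. Illustration if 10.3 is used as a filter: binormal model**

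Inputs from the documents: AUC 0.725 and the 1:2 ratio (15.2). Assumptions:

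- The marker is equal-variance normal in each group, with lower values in responders.
- 0.725 applies to the full marker range.
- 63% are at or below low-normal on each marker. This borrows 14% + 49% from the stroke-rehabilitation figures in Background.
- The two markers have a within-group correlation of 0.3 to 0.7.
- A Veteran is seen if either marker qualifies.

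Separation: d = √2 × Φ⁻¹(0.725) = 0.845. Unselected, the Liu point is midway, so sensitivity = specificity = Φ(0.845/2) = 66%.

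Simulated with 2,000,000 Veterans:

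| Correlation | Share seen | AUC | True sensitivity at the selected-sample cut-point |
|---|---|---|---|
| 0.3 | 80% | 0.676 | 57.4% |
| 0.5 | 77% | 0.673 | 56.7% |
| 0.7 | 74% | 0.671 | 54.5% |

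About 5-10% of responders and 27-34% of non-responders go unrated. The selected cut-point lies below the low-normal limit, so every responder under it is seen. In-sample sensitivity is therefore true sensitivity divided by the share of responders seen: 57.4/0.95 or 54.5/0.90, about 60-61%. It overstates the true value.

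**4. A model that behaves differently**

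Suppose response is 70% below the 25th percentile and constant above it, one-third respond overall, and the lowest 63% are seen.

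- Background response: (0.3333 − 0.25×0.70)/0.75 = 21.1%.
- Unselected, cut at the 25th percentile: sensitivity 0.175/0.3333 = 52.5%; false-positive rate 0.075/0.6667 = 11.25%; AUC (1 + 0.525 − 0.1125)/2 = 0.71.
- Selected, same cut: sensitivity 0.175/(0.175 + 0.38×0.211) = 68.6%; false-positive rate 0.075/(0.075 + 0.38×0.789) = 20.0%; AUC (1 + 0.686 − 0.200)/2 = 0.74.

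Here the AUC rises and the cut-point does not move, yet in-sample sensitivity is still too high (68.6% against 52.5%). With the threshold at the 40th percentile the AUC falls from 0.83 to 0.78, cut-point unchanged. With it at the 14th, the cut-point moves down.

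**The case against.** The strongest reply is that the sentence says all such Veterans will be seen; it does not say only they will. Read with its heading, Study Duration, the data section and the consent text, it bars nobody. Section 10.1 also keeps the remaining data when a treated Veteran's thiamine values are lost, which fits poorly with a biomarker gate. The low or low-normal wording may simply echo the Aim 2 case definition. All of this stands, and it makes the symptom-based reading the likelier one. It does not remove the conflict, because the sentence is 10.3's only list of attendees and 15.2 names no set that would settle the matter.

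Stronger readings that a reader might infer, and why they fail:

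- *Sensitivity drops from 66% to 49% and no cut-point above the low-normal limit can be found.* This needs the analysed marker itself to qualify. In that model at 63% retained, AUC is 0.66, and 18% of responders and 47% of non-responders are unrated. Over 40-80% retained, AUC is 0.63-0.68 and true sensitivity 35-58%. The sentence does not require this. If either marker suffices, 15-22% of those seen are above the limit on the analysed marker.
- *The AUC must fall and the cut-point must move down.* The threshold model shows otherwise.
- *The aim of beating the laboratory limit is defeated.* In the binormal model the laboratory limit has 27% sensitivity if 14% are low and 44% if 25% are low. The either-marker cut-point exceeds both.
- *The primary prevalence is biased.* The primary outcome in 15.1 already requires a low or low-normal marker, so Veterans normal on both could not be cases under it. Section 15.1 also defines a TDD without naming a marker; that is a separate question of definition.
- *Every other section sets a symptom rule.* Table 3 gives timing and 10.2 gives treatment duration for the severe group. They merely mention no biomarker.

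**Conclusion.** The inconsistency is real and minor. It has no effect under the symptom-based reading, which most of the protocol supports.

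If 10.3 is used as a filter, symptomatic treated Veterans normal on both markers have no response rating, and the exploratory Aim 2 ROC analysis is run on a sample selected on the marker. Its sensitivity and specificity would not describe all symptomatic treated Veterans. In the models tried, in-sample sensitivity overstated true sensitivity.

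The binormal loss in step 3 (about 8 to 11 percentage points of true sensitivity) is an illustration. Low normal has no numeric limit in the documents, the 63% comes from another population, the marker correlation is assumed, and 15.2 itself says nothing informs its AUC parameters. The direction and size of any change in AUC and cut-point depend on the model.

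**What to change.** - Reconcile the 10.3 sentence with its heading, Study Duration, the consent text and the data section, so that among Veterans started on thiamine for symptoms the Visit 3 outcome assessment does not depend on the biomarker result.
- State in 15.2 that the Aim 2 ROC set is all symptomatic treated Veterans with a Visit 3 rating, not restricted by marker level.
- Reconcile 10.3 with Study Duration on whether Veterans with low results and no symptoms attend Visit 3.

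The cost is a short wording amendment and one sentence in 15.2. Some Visit 3 attendances at $200 each would follow, but Study Duration already expects them. No treatment rule needs to change for this. The wording should be settled while visits can still be held, because a missed Visit 3 rating cannot be recovered later.

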Measurements: The **primary outcome** of this arm is to determine if there are differences in markers of inflammation as evidenced by hs-CRP and fibrinogen between TDD and non-TDD hospitalized Veterans. Presence of inflammation will be defined as hs-CRP higher than upper limits of normal 0.75 milligrams/deciliter (mg/dL), or fibrinogen higher than the upper limits of normal 471 mg/dL. Individuals will also be considered to have inflammation if they are diagnosed with one of the AICs or CICs previously described.

Statistical analysis: The presence or absence of AICs and CICs among those with and without TD (defined as treatment responsive TD or abnormal thiamine levels based on clinical laboratory standards) will be evaluated by Chi-square or Fisher's exact test depending on assumptions being met. An assessment of total number of AICs and/or CICs between TD and non-TD patients will be assessed using the student's T-test or non-parametric methods depending on necessary assumptions being met. To evaluate if biomarkers of inflammation (hs-CRP and/or fibrinogen) are associated with presence or absence of TD we will compare levels between these two groups. If group sizes are large enough, we will attempt to develop exploratory multivariate models to identify AICs, CICs, and inflammation markers which are associated with TDD status. As no studies have reported on inflammatory markers, AICs, and CICs and thiamine deficiency, this is an exploratory aim for which we have no data to estimate a priori sample size requirements.

Resources Available

The VA hospital is a 64-bed general medical and surgical facility. There are typically 10 patients admitted to the hospital daily and we expect no trouble enrolling 300 patients in our study over 12 months. [name] will dedicate 3/8ths of her full-time employment with the VA managing this project. We will have a full-time research coordinator and a half time Health Systems Specialist (PA or ARNP) performing the day-to-day operations of the study. [name] will train both employees on the research purpose and protocol and assign duties as appropriate to their background and training in completion of the study. Veteran participants will be given a detailed description of their role in the research project and will be provided phone numbers to contact study personnel in the event of an adverse outcome or symptom. All medical and psychological care will be provided through the VA for adverse events.

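### Treatment response at Visit 3 has no written threshold and is rated when thiamine results are expected to be available to the examiner, so knowledge of the level can distort the level-response association in either direction

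*Combined protocol and SAP*

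**What the plan says.** **The rating.** Section 10.3 states: "We will repeat the symptom and function survey and repeat the standardized physical assessment". It then says "We will categorize changes in symptoms and signs as" one of two levels, "no or minimal improvement, or noticeable improvement". It does not say how much change counts, on which instrument, or how mixed changes are resolved.

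**The instruments.** Section 10.2 provides structured measures: "mental status exam using the Montreal Cognitive Assessment (MoCA); delirium screen using the 4AT", a graded strength scale, a checklist of signs and symptoms, and a review of ADLs and IADLs.

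**The timing.** Thiamine biomarkers are drawn at Visit 1. Section 10.2 says "We anticipate return of lab biomarker results 7-10 days after they are drawn", after which Veterans missed by clinical screening are contacted and started on thiamine. Visit 3 comes after two weeks of treatment.

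**Access to results.** Section 10.1 places results in the electronic medical record, from which they "will be extracted by the study coordinator and stored in a de-identified database". Under Sharing of Results with Participants, the team telephones Veterans with low levels. Informed Consent Process rules out blinding of participants. Masking of the examiner is not mentioned anywhere.

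**The use of the rating.** Section 15.1 makes response to thiamine part of the primary outcome definition and of the TDD definition. Section 15.2 compares thiamine levels between responders and non-responders. It then derives the cut-point, sensitivity, specificity and AUC with response as the reference classification, and calls this aim exploratory.

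**The concern.** A reference classification made with knowledge of the marker under evaluation can take on a relation to that marker which the patients' course does not contain. Two features add to the risk here: the category is left to judgement, and there is no untreated or placebo group against which to see the effect.

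The protocol also holds expectations tied to the level. Hypothesis 2 expects improvement in the low-normal range, which could raise ratings there. The usual expectation that the most deficient patients benefit most could raise ratings in the low range. Either would affect the test of Hypothesis 2 and every accuracy estimate in section 15.2. The same rating also decides who meets the primary case definition.

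**Working it through.** **1. Order of events.** Results are expected by day 7-10 after a Visit 1 draw. For most Veterans thiamine starts at Visit 2 or discharge, and Visit 3 follows at least 14 days of it. Since 14 exceeds 10, results are normally back before the rating. For Veterans started on thiamine because of the result, the team knows the result by definition.

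**2. The plan's own Aim 2 figure.** Section 15.2 asks for 19 responders and 38 non-responders to detect an AUC of 0.725 against 0.50, with alpha 0.05 and what is read here as power 0.80. The Hanley-McNeil variance is

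Var(A) = [A(1-A) + (n1-1)(Q1-A²) + (n0-1)(Q2-A²)] / (n1·n0), with Q1 = A/(2-A) and Q2 = 2A²/(1+A).

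- A = 0.50: (0.25 + 18×0.0833 + 37×0.0833)/722 = 0.00669, SE 0.0818.
- A = 0.725: (0.1994 + 18×0.0430 + 37×0.0838)/722 = 0.00564, SE 0.0751.
- Two-sided power: Φ[(0.225 - 1.96×0.0818)/0.0751] = Φ(0.86) = 80.5%.

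The figure reproduces, and the total of 57 is used below.

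**3. Illustration with no true link.** These inputs are assumptions, not figures from the documents: 28 low and 29 low-normal Veterans, an overall rate of improvement calls of 1/3 (the plan's 2:1 ratio) or 1/2, and calls shifted up by d in the low group and down by d in the low-normal group. The gap between groups is 2d. With near-equal groups,

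AUC of the low flag = 0.5 + [P(low | responder) - P(low | non-responder)]/2.

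| Overall rate | Gap | Improved, low vs low-normal | P(low, responder) | P(low, non-responder) | AUC |
|---|---|---|---|---|---|
| 1/3 | 20 points | 43% vs 23% | 0.65 | 0.425 | 0.61 |
| 1/2 | 20 points | 60% vs 40% | 0.60 | 0.40 | 0.60 |
| 1/3 | 40 points | 53% vs 13% | 0.80 | 0.35 | 0.725 |
| 1/2 | 40 points | 70% vs 30% | 0.70 | 0.30 | 0.70 |

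**4. False-positive rate of the planned test.** Section 15.2 plans a Kruskal-Wallis comparison of levels between responders and non-responders. It was simulated on ranked levels with 40,000 data sets per setting. With no gap it is positive about 5% of the time. With the 20-point gap it is positive about 25-28% of the time. The plan mentions a multiplicity correction without specifying it. If that is Bonferroni for two biomarkers (an assumption), the rate is 17-19%.

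**5. The opposite direction.** If the low-normal group is favoured by the same 20 points, symmetry gives an AUC of 1-0.61 to 1-0.60, that is 0.39-0.40. A real relation between low levels and response would then be weakened or hidden.

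**6. Effect on the overall response rate.** In the 20-point scenario it is (28×0.433 + 29×0.233)/57 = 33.2% against 33.3%, or (28×0.60 + 29×0.40)/57 = 49.8% against 50%. It is essentially unchanged.

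**The case against.** The other side has several sound points.

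- **Availability is not use.** The documents show that results are there to be seen, not that the examiner reads them. The absence of masking is inferred from silence together with open access.
- **Attendance does not reveal the group.** Section 10.3 says "All Veterans with low biomarkers OR low normal biomarkers and clinical symptoms of TDDs that were initiated on replacement will be seen", so both low and low-normal Veterans attend, and that is the contrast at issue. Informed Consent Process and Study Duration tie follow-up to symptoms instead, so the text is not uniform on who attends.
- **The examination is standardised.** Only the step from findings to the two categories lacks an anchor.
- **The cut-point work is labelled exploratory**, which limits the weight of its AUC.
- **The assumed gaps are not supported by any figure in the plan.** An AUC of 0.725 needs 53% against 13% called improved with no true difference, which is a large bias.

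These points limit how strongly the concern can be put. They do not supply a response rule or a safeguard.

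A reader might go further in three ways that the documents do not support. One is that prevalence is inflated: step 6 shows that a level-dependent shift can leave it unchanged, and inflation would need general optimism about treatment, which is a different mechanism. Another is that the cut-point is pulled toward the current laboratory limit: Hypothesis 2 points the other way, so the direction is unknown. The third is to quote 36-38% false positives for the 20-point gap: that comes from a z test on a dichotomised marker, which is not the planned analysis.

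**Conclusion.** The point holds as a weakness of design that should be corrected. The rating that serves as reference for Aim 2, and as part of the primary case definition, has no written threshold and is made when the thiamine level is expected to be available, with nothing to keep it from the examiner. Knowledge of the level can therefore create, exaggerate or hide a level-response association.

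How much this would matter cannot be derived from the documents. Under the assumed 20-point gap with 57 Veterans, chance findings on the planned test rise from about 5% to about 25-28% (17-19% with the assumed two-biomarker correction), and the AUC is about 0.60-0.61. Only a 40-point gap brings the AUC to 0.70-0.725, about the plan's target. The calculation shows what such bias could do, not that it will occur, and it supports no statement about the direction of error in prevalence or in the cut-point.

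**What to change.** 1. **Write the response rule.** Define the improved category by change from Visit 2 to Visit 3 in the data already collected: MoCA, 4AT, strength grade, ADL/IADL and the symptom checklist. State how mixed changes are resolved. Fix the rule before response is analysed against thiamine levels, and apply it to all Veterans, including any already seen.
2. **Lock the rating first.** For remaining Visit 3s, the coordinator, who already extracts the results, holds them and handles calls and booking. The staffing exists: "We will have a full-time research coordinator and a half time Health Systems Specialist (PA or ARNP"), in addition to the principal investigator. Result-driven contact that needs a clinician goes to whichever of the investigator or practitioner will not examine that Veteran at Visit 3. The examiner enters and locks the category before opening the levels.
3. **Record and test.** Note for each rating whether the examiner knew the level, and repeat the cut-point analysis without the unmasked ratings.

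The cost is protocol and analysis-plan wording and a division of tasks among existing staff, with no extra visit or procedure and no change to any treatment rule. The limits should be stated. Masking is procedural and imperfect, because results sit in the medical record, participants learn their own results, and a late start of thiamine can signal a low value. Masking to level does not remove general optimism from open-label treatment. The written rule keeps its value even where masking fails.
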